### **4.3 EXCLUSION CRITERIA**

We are unable to recruit participants who at the time of recruitment are experiencing severe pain or oedema in the arm affected by their stroke. This is because their course of rehabilitation is different from a stroke survivor who isn't affected by these conditions, hence a comparison between samples would be impossible.

### **4.4 WITHDRAWAL CRITERIA**

- Participants are free to withdraw from the study at any time. However, anonymised activity data collected may still be used for data analysis as this is unlinked of any patient identifiable information.
- Participants will be withdrawn from the study if
  - they develop ongoing arm pain scoring 3/10 or more on the VAS or swelling in the affected arm during the study that is reported to be negatively impacted by wearing the tracker and taking part in the study.
  - Their treating therapist/medical professional is concerned about them participating.
  - Are not engaging with the process.

- They become unable to participate due to a change in their health or any other force majeure circumstances.
- If at any point the researchers become concerned about a participant's cognition or communication then the researchers will, in the first instance, discuss this with the participant's therapist, or if this is not possible, the participant will be withdrawn from the study.

Participants will be responsible for reporting a change in symptoms (pain, swelling, etc.) to researchers during the study.

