#### **Outcomes**

Feasibility outcomes including the percentage of patients eligible, recruited and completing the 14-week intervention.

Clinical outcomes (such as Fugl-Meyer, Motor Activity Log, Patient Activation Measure, EQ-5D-5L, Friends & Family test, Montreal Cognitive Assessment, Visual Analog Scale Pain, Rankin Scale, etc.) will be collected to identify an appropriate primary outcome, and to estimate parameters for a sample size calculation.

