### **7.2 CONSENT**

Consent to enter the study must be sought from each participant only after a full explanation has been given, an information leaflet offered and time allowed for consideration.

For patients:

Verbal consent will be provided to the therapists and then the researchers will obtain written consent.

For family/carer: Written consent will be sought.

For therapist and frontline healthcare staff: Written consent will be sought.

The right of the participant to refuse to participate without giving reasons must be respected. After the participant has entered the study the clinician remains free to give alternative treatment to that specified in the protocol at any stage if he/she feels it is in the participant's best interest, but the reasons for doing so should be recorded. In these cases the participants remain within the study for the purposes of follow-up and data analysis. All participants are free to withdraw at any time from the protocol treatment without giving reasons and without prejudicing further treatment.

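### Section 4.4 ends study participation for non-engagement, pain or swelling, and clinician concern, is not reconciled with section 7.2, and may select the week 7 and 13 outcomes towards people who engage with and tolerate OnTrack

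*Combined protocol and SAP*

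**What the plan says.** Section 4.4 (Withdrawal criteria) sets its exit at the level of the study: "Participants will be withdrawn from the study if" one of a list of conditions applies. Three matter here:

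- Pain or swelling: ongoing arm pain of 3/10 or more on the VAS, or swelling, where it is described as "negatively impacted by wearing the tracker and taking part in the study", so that the device and participation are named together.
- Clinician concern, worded as "Their treating therapist/medical professional is concerned about them participating", with no requirement that the concern be about the device rather than the study.
- Non-engagement, worded as "Are not engaging with the process", for which no threshold is given.

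The section says nothing about outcome measures after withdrawal. Its only data provision accompanies voluntary withdrawal and covers anonymised activity data already collected.

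Section 7.2 (Consent) treats the matter differently. It says "the clinician remains free to give alternative treatment to that specified in the protocol at any stage", with the reasons recorded, and then: "In these cases the participants remain within the study for the purposes of follow-up and data analysis". It also says that every participant may leave the protocol treatment at any time, without saying whether assessments then continue.

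Under Dose in section 3, outcome measures are taken at week 0 and repeated at weeks 7 and 13. Under Outcomes, the plan lists "Feasibility outcomes including the percentage of patients eligible, recruited and completing the 14-week intervention", and says the clinical measures "will be collected to identify an appropriate primary outcome, and to estimate parameters for a sample size calculation". A sample size estimate for a definitive RCT is one of the feasibility assessment criteria.

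**The concern.** Stopping the intervention and ceasing to provide outcome data are different events, and a definitive trial needs to know about each. Section 4.4 joins them. On its natural reading, someone withdrawn before week 7 loses both remaining outcome assessments, and someone withdrawn after week 7 loses week 13. Week 0 data are unaffected.

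Two things are at stake. First, the week 7 and 13 values from which an RCT primary outcome and its variability are to be judged may be selected towards people who engage with and tolerate the system. Second, for those withdrawn under 4.4 and not retained by 7.2, the study cannot show how many could still have given a week 13 outcome. An RCT that follows people after they stop treatment needs that quantity for its missing-outcome allowance. The planned intervention-completion rate does not supply it.

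**Working it through.** **The two sections side by side**

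| Situation | Section 4.4 | Section 7.2 | Outcome assessment afterwards |
|---|---|---|---|
| Pain or swelling linked to tracker and participation | Leaves the study | Not addressed, unless the clinician changes treatment | None provided for |
| Non-engagement | Leaves the study | Not addressed | None provided for |
| Clinician concern leading to alternative treatment | Leaves the study | Stays in follow-up and analysis | No rule says which section governs |
| Participant chooses to leave protocol treatment | Addresses withdrawal from the study only | Permitted | Not stated |

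**The plan's own figure**

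Inputs: 12 to 30 completers and 50% drop-out (section 6); 24 to 38 starters (section 3, Recruitment, and section 6).

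- Lower bound: 12 / (1 − 0.5) = 24, which reproduces.
- Upper bound: 30 / (1 − 0.5) = 60, so 38 is not an inflation of 30. However, 38 × 0.5 = 19 completers, which lies within 12 to 30, and section 6 also cites time and budget. The range fits its stated reasoning.

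**Illustration of size**

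The 50% is not broken down by reason, so the number affected cannot be derived. Let k be the number of expected drop-outs who could have been assessed after stopping OnTrack. This is an assumption with no source in the documents. Assume also that drop-out means no week 13 data. Then missing at week 13 = (0.5N − k) / N, and the RCT inflation factor = 1 / (1 − missing).

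| k (assumed) | N = 24: missing | Factor | N = 38: missing | Factor |
|---|---|---|---|---|
| 0 | 12/24 = 50.0% | 2.00 | 19/38 = 50.0% | 2.00 |
| 1 | 11/24 = 45.8% | 1.85 | 18/38 = 47.4% | 1.90 |
| 2 | 10/24 = 41.7% | 1.71 | 17/38 = 44.7% | 1.81 |
| 4 | 8/24 = 33.3% | 1.50 | 15/38 = 39.5% | 1.65 |
| all drop-outs | 0/24 = 0% | 1.00 | 0/38 = 0% | 1.00 |

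The last row is a logical limit, not an expectation.

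Outcome sets lost are k if everyone leaves after week 7, or 2k if everyone leaves before it. Scheduled sets are 2N = 48 or 76. At k = 4 that is 4 to 8 sets: 8.3% to 16.7% of 48, or 5.3% to 10.5% of 76. At k = 0 it is none.

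**Sampling uncertainty**

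The exact (Clopper-Pearson) 95% interval is 29.1% to 70.9% for 12/24, a factor of 1.41 to 3.43. For 19/38 it is 33.4% to 66.6%, a factor of 1.50 to 3.00. Every row from k = 0 to k = 4 lies inside these intervals.

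**The case against.** Four objections carry weight.

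*Section 7.2 already makes the distinction.* It retains people given alternative treatment and recognises withdrawal from treatment for everyone. This stands. A reader might infer from 4.4 alone that the plan cannot separate discontinuation from outcome attrition at all; 7.2 shows that to be too strong. But 7.2 does not say that people who leave treatment are still assessed, and it does not reach researcher-initiated withdrawal for non-engagement, pain or swelling.

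*The triggers concern participation itself.* The pain criterion names both the tracker and taking part, the clinician's concern is about participating, and non-engagement is with the process as a whole. Full exit is right for some of these people, and some non-engagers would not attend an assessment anyway. This also stands, and it is why the group who could still be assessed may be small or empty. It does not justify automatic exit for those who are willing and able.

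*Nothing demonstrable changes.* A reader might infer that the sample size of 24 to 38 is wrong, or that an estimate of effect is biased. Neither follows. The range fits its stated reasoning, and the Study Design section says the study is non-randomised and not meant to measure effectiveness. The direction of any bias in the outcome parameters cannot be derived either.

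*Transfer to an RCT is limited.* There is no comparator here from which to learn control-arm retention, and the protocol does not name a missing-outcome rate among its intended parameters. This stands, and it limits how the extra rate should be used.

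**Conclusion.** The point holds as a modest design weakness. Section 4.4 mandates study-level exit, section 7.2 would keep some of the same people in follow-up, and no rule says which applies. For people stopped for non-engagement, pain or swelling, no part of the protocol provides continued outcome assessment. The week 7 and 13 data may be selected as a result, and for those withdrawn under 4.4 and not retained by 7.2, stopping the intervention and losing outcomes are counted together.

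The size is unknown and may be zero. The illustration rests on an assumed k and on equating drop-out with no week 13 data, and its shifts up to k = 4 cannot be told apart from sampling error. The gain from a change is a separately measured rate and possibly less selection, not better precision. The reading that full exit is what 4.4 intends rests on its wording, since it is silent on outcome measures.

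**What to change.** In section 4.4, keep the triggers but have them stop OnTrack rather than end study participation automatically, and state that this applies together with section 7.2. Offer the remaining scheduled week 7 and 13 outcome measures where the participant agrees and tolerates them. Do not offer the week 13 activity trackers to anyone stopped for pain or swelling.

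End participation fully if:

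- consent is withdrawn;
- the participant is unable to take part;
- assessment aggravates symptoms;
- the clinician's concern covers study participation or the assessments; or
- a concern about cognition or communication is unresolved.

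Report the week 13 outcome-completion rate over all starters, separately from the planned intervention-completion rate. Use it to inform the RCT's missing-outcome allowance, with its wide interval shown and labelled as single-arm evidence.

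The cost is a wording amendment, one more reported rate and at most 2k already-scheduled assessments: none at k = 0, and up to 2 × 4 = 8 at k = 4 (assumed). These visits fall on a study whose size was already limited by time and budget. No new procedure is needed, and some people will decline.

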#### 4.5 DISTRESS PROTOCOL

##### Users (patients, staff, family/carer)

- In the event that a participant communicates (verbally or body language) that they are becoming distressed the session will be temporarily stopped and participant given a moment and then asked if they would like to continue.
  - If the response is that they would like the session to finish it will stop immediately. The researchers will ask the participant what they would like to do. (e.g. If they would like to be left alone, have a family/friend called, or stay with the researchers or in the case of staff have a colleague or manager contacted.)
  - If the response is that they would like the session to continue it will do so. However, if on a second occasion the participant becomes distressed the session will stop immediately. At this point the participant will be asked what they would like the researchers to do. (e.g. If they would like to be left alone, have a family/friend called, or stay with the researchers or in the case of staff have a colleague or manager contacted.)

##### Researchers

- The researchers will consider the number of patient facing sessions that they complete per day/week to take into consideration the exposure to potentially distressing information.
- If the researchers at any point become distressed during a session then they will look to stop the interview and seek the necessary support (discussion with a colleague, line manager, etc.).

### 5. ASSESSMENT AND FOLLOW-UP

Participants will be involved in the study described above, their involvement lasting typically 14 weeks. No follow up after this point is planned.

### 6. STATISTICS AND DATA ANALYSIS

#### Sample Size

24-38 patients.

Literature advocates a sample size of 12-30 participants at the completion of a feasibility study. A 50% drop out rate is expected. We have taken these two points into consideration in addition to what is realistic within our time frame/budget to come to our current sample size.

### **Data Analysis**

Analysis will be completed on the parameters and implementation of the study in addition to the usability of OnTrack.

Data collected for the process evaluation will capture changes over time and will be a combination of qualitative data from interviews with stroke participants, therapists and frontline staff to explore their experiences of using OnTrack, as well as quantitative data on usage of OnTrack and the self-reported SUS. OnTrack therapy support sessions will be monitored through a fidelity checklist and observations. Interview data will undergo thematic analysis.

Data will be analysed for any association between the feasibility of the intervention and stroke subtype, patient demographics, stroke disability, and the amount of physiotherapy patients receive during the intervention period.

## **7. REGULATORY ISSUES**

### **7.1 ETHICS APPROVAL**

The Chief Investigator will seek ethical approval from the NHS Research Ethics Committee and the Health Research Authority. The study will be conducted in accordance with the recommendations for physicians involved in research on human subjects adopted by the 18th World Medical Assembly, Helsinki 1964 and later revisions.

### **7.2 CONSENT**

Consent to enter the study must be sought from each participant only after a full explanation has been given, an information leaflet offered and time allowed for consideration.

For patients:

Verbal consent will be provided to the therapists and then the researchers will obtain written consent.

For family/carer: Written consent will be sought.

For therapist and frontline healthcare staff: Written consent will be sought.

The right of the participant to refuse to participate without giving reasons must be respected. After the participant has entered the study the clinician remains free to give alternative treatment to that specified in the protocol at any stage if he/she feels it is in the participant's best interest, but the reasons for doing so should be recorded. In these cases the participants remain within the study for the purposes of follow-up and data analysis. All participants are free to withdraw at any time from the protocol treatment without giving reasons and without prejudicing further treatment.

### **7.3 CONFIDENTIALITY**

The Chief Investigator is responsible for preserving the confidentiality of participants taking part in the study.

Researchers will have patients' names, contact numbers, emails and home addresses for the purposes of arranging visits. This information will be stored securely on Imperial College computers.

Participants will be assigned a participant identification number that will be used in place of their name wherever possible.

The documents that links the patient's name to the ID number will be stored on a password protected university computer.

Images, videos and audio recordings may be taken at any stage of the study with the participants consent. Media will be stored securely on a password protected device. Audio recordings maybe transcribed by an external service - with patient identifiable information removed ahead of this. Photographs taken will be anonymised as soon as possible. Videos will exclude participants' faces.

Direct quotes may be used alongside a participant characteristic (e.g. Patient (M/F) had a stroke 6 weeks ago and could not use his arm) however participant identifiable information will not be used alongside quotes.

There will be a combination of patient information stored on paper (e.g. consent forms) and electronically (e.g. patients address). Paper documentation will be stored in a locked cupboard inside a locked office at Imperial College London only accessible to the researchers. Electronic information will be stored on University computers that are also password protected.

Data and all appropriate documentation will be stored for a minimum of 10 years after the completion of the study in line with Imperial College London policy.

#### **7.4 INDEMNITY**

Imperial College London holds negligent harm and non-negligent harm insurance policies that apply to this study.

#### **7.5 SPONSOR**

Imperial College London will act as the main Sponsor for this study. Delegated responsibilities will be assigned to the NHS trusts taking part in this study.

#### **7.6 FUNDING**

This project is funded by the Helix Centre and NIHR Imperial Biomedical Research Council  
No participant payments or incentives will be given.

#### **7.7 AUDITS**

The study may be subject to inspection and audit by Imperial College London under their remit as sponsor and other regulatory bodies to ensure adherence to GCP and the NHS Research Governance Framework for Health and Social Care (2nd edition).

### **8. STUDY MANAGEMENT**

The day-to-day management of the study will be coordinated through the Helix Centre by My [name] (contact details above).

### **9. PUBLICATION POLICY**

The researchers will seek to publish their work through publications in peer-reviewed journals.

